# **8. PHARMACEUTICAL INFORMATION**

A list of the adverse events and potential risks associated with enoxaparin administered in this study can be found in Section 7.1.

## **8.1 *Enoxaparin***

### **8.1.1 Description**

Enoxaparin sodium is obtained by alkaline depolymerization of heparin benzyl ester derived from porcine intestinal mucosa. Maximum anti-Factor Xa and anti-thrombin (anti-Factor Iia) activities occur 3 to 5 hours after subcutaneous injection. Mean absolute bioavailability of enoxaparin, after 1.5 mg/kg given subcutaneously, based on anti-Factor Xa activity is approximately 100% in healthy subjects. After repeated subcutaneous administration of 40 mg once daily, the steady state is reached on day 2 with an average exposure ratio about 15% higher than after a single dose. Steady-state enoxaparin activity levels are well predicted by single-dose pharmacokinetics. Following subcutaneous dosing, the apparent clearance (CL/F) of enoxaparin is approximately 15 mL/min of enoxaparin. Enoxaparin is primarily metabolized in the liver by desulfation and/or depolymerization to lower molecular weight species with much reduced biological potency. Total renal excretion of active and non-active fragments represents 40% of the dose.

**8.1.2 Form**

Enoxaparin is manufactured for subcutaneous injection. Enoxaparin in solution is supplied at varying volumes and concentrations, e.g. 100mg/ml. Enoxaparin is available through various manufacturers and suppliers.

**8.1.3 Storage and Stability**

Recommended storage is 25°C (77°F); excursions permitted to 15-30°C (59-86°F)..

**8.1.4 Compatibility – Normal saline**

**8.1.5 Handling**

Care should be taken when handling needles.

**8.1.6 Availability**

Enoxaparin is available from various manufacturers and will be purchased and prepared by the research pharmacy. Enoxaparin will be covered by the grant and provided free of charge.

**8.1.7 Preparation**

The QACT office will inform the research pharmacy of treatment allocation (Arm A or Arm B). The research pharmacy will not be blinded to treatment arm. Appropriate dose of enoxaparin will be aliquoted into syringes and diluted to 1 ml in normal saline. The syringe should not list the enoxaparin dosage.

**8.1.8 Administration**

Participants should be lying down and enoxaparin administered by subcutaneous injection into the abdominal wall on a once daily basis.

**8.1.9 Ordering**

An order will be written and signed by an authorized provider.

**8.1.10 Accountability**

The investigator, or a responsible party designated by the investigator, should maintain a careful record of the inventory and disposition of the agent using the NCI Drug Accountability Record Form (DARF) or another comparable drug accountability form. (See the NCI Investigator's Handbook for Procedures for Drug Accountability and Storage.)

**8.1.11 Destruction and Return**

Any unused study drug will be destroyed on site per standard operating procedures.

**9. BIOMARKER, CORRELATIVE, AND SPECIAL STUDIES**

## **9.1 Biomarker Studies**

We previously demonstrated the predictive value of circulating tissue factor bearing microparticles in cancer outpatients. We will evaluate if the number of tissue factor bearing microparticles upon hospitalization predicts thrombotic risk. Microparticles will be isolated from plasma by differential centrifugation. We modified an impedance-based flow cytometry system (Beckman Coulter SC Quanta) in order to address the shortcomings of standard light scatter based flow cytometry in the measurement of small ( $<1\text{ }\mu\text{m}$ ) particles.[21] Using this methodology we observed a significant correlation between elevation in tissue factor bearing microparticles and the development of cancer-associated thrombosis.[21, 26]

Based on animal models suggesting that tumor derived tissue factor bearing microparticles accumulate at the site of a developing thrombus through the binding of PSGL-1 with P-selectin, we will evaluate whether subpopulations of TF-bearing microparticles are associated with thrombosis in hospitalized cancer patients. By flow cytometry, we will determine the percentage of TF-bearing microparticles co-expressing the PSGL-1, MUC1, and/or CD14 antigens.

D-dimer is a degradation product of cross-linked fibrin and is the most widely utilized sensitive biomarker to exclude venous thromboembolic events.[27, 28] Utility of D-dimer alone to predict thrombosis in cancer patients is limited due to poor specificity especially using standard cut-offs.[29] D-dimer will be measured by using a commercially available immunoassay (Roche Diagnostics). We will analyze the association between thrombosis and elevated D-dimer values based on standard cutoff of  $>500\text{ng/L}$ , 75th percentile based on measurements using stored plasma from cancer patients[21, 29] or age adjusted-cutoff which was recently demonstrated to improve assay specificity in a large cohort of patients (including 429 patients with active malignancy).[28] In order not to confound study outcomes, D-Dimer measurements will be performed centrally at BIDMC after the completion of the trial and will not be recorded in the participant's medical record.

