13.6.3 Biomarkers: The primary analysis of each of the biomarkers is to identify whether any of the pre-defined cutoff values are sensitive for VTE in the high risk cancer patients randomized to fixed-dose enoxaparin. Biomarkers such as tissue factor bearing microparticles and D-dimer have previously demonstrated low positive predictive values but high negative predictive values in cancer cohorts.[26, 28, 29] The combination of high tissue factor bearing microparticles ( $>3.5 \times 10^4$  microparticles/ $\mu$ l, the top tercile of tissue factor-bearing microparticle concentrations from the reference specimens) and elevated D-dimer further improved the sensitivity and specificity of the individual assays.[26] We will evaluate whether any of the individual biomarkers or combination of biomarkers are sensitive to identify all VTE diagnosed in the high risk cancer patients randomized to fixed-dose enoxaparin. We plan to assess the 2 by 2 contingency table distributions using the pre-defined cut-off values in order to evaluate the classification probabilities (particularly specificity and sensitivity) based on the chosen cut-off. The top tercile of tissue factor-bearing microparticle concentrations and D-dimer or the age-adjusted D-dimer cut-off of the study cohorts will be also considered to evaluate the classification probabilities of the classification model. Fine and Gray univariate regression models will be used to assess the impact of each biomarker classification on the risk of developing VTE. In addition, using regression models we aim at assessing whether there is an association between the scores in the scoring systems and the biomarkers. As this is the initial exploratory evaluation of PSGL-1+ microparticles and thrombosis, additional validation in the phase III trial will be required.

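### The standard D-dimer cut-off in section 9.1 is printed as >500 ng/L (0.5 ng/mL), probably a thousandfold unit slip that would leave this one exploratory cut-off with no negative patients

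*Combined protocol and SAP*

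**What the plan says.** Section 9.1 (Biomarker Studies) sets out how D-dimer will be classified: "We will analyze the association between thrombosis and elevated D-dimer values based on standard cutoff of" >500 ng/L. It lists two alternatives, a 75th "percentile based on measurements using stored plasma from cancer patients[21, 29] or age adjusted-cutoff", neither with a number or unit. It describes D-dimer as a widely used sensitive marker for ruling out VTE, and adds: "Utility of D-dimer alone to predict thrombosis in cancer patients is limited due to poor specificity especially using standard cut-offs". The assay is identified only as a commercial immunoassay, with no reporting unit or measuring range. Measurement is central and takes place after the trial is complete.

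Section 13.6.3 (Biomarkers) uses these thresholds. The main biomarker analysis is to "identify whether any of the pre-defined cutoff values are sensitive for VTE in the high risk cancer patients randomized to fixed-dose enoxaparin". The method is stated as "We plan to assess the 2 by 2 contingency table distributions using the pre-defined cut-off values in order to evaluate the classification probabilities", followed by univariate Fine and Gray models for each biomarker classification. A further set of cut-offs is added: "The top tercile of tissue factor-bearing microparticle concentrations and D-dimer or the age-adjusted D-dimer cut-off of the study cohorts will be also considered". On past performance, the section says that markers such as tissue factor bearing microparticles and D-dimer "have previously demonstrated low positive predictive values but high negative predictive values in cancer cohorts". The microparticle threshold is given there with a number and a unit; D-dimer is described only as elevated.

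**The concern.** The printed threshold is an operative analysis constant, not background text. It is one of the pre-defined cut-offs that 13.6.3 will judge by whether it picks up every VTE. At 0.5 ng/mL it sits poorly with the documents' own account of the marker, because a test used to rule out VTE, with high negative predictive value, must classify some patients as negative.

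If no patient falls below the printed value, this cut-off meets the sensitivity aim automatically and tells the reader nothing. If the analyst instead quietly applies a different unit, the analysis departs from the only D-dimer number that was fixed in advance. Either way, pre-specification is lost for this cut-off.

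**Working it through.** **Inputs.** Cut-off >500 ng/L (9.1). Arm A size 25 and assumed VTE incidence 12% (13.2). The D-dimer distribution is not in the documents and is assumed below.

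**Reproducing the plan's figures.** The cut-off is a stated constant, so there is nothing to re-derive. The two inputs from 13.2 are consistent: 3/25 = 12%, with an exact 90% interval of 3.35% to 28.17%, against the stated 3.3% to 28.2%.

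**Unit conversion.** 500 ng/L ÷ 1000 mL per L = 0.5 ng/mL. If per millilitre was meant, the cut-off is 500 ng/mL = 500,000 ng/L, and 500,000 ÷ 500 = 1000.

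**How many patients would be negative?** Assume lognormal D-dimer with median m and log-SD s. Then P(below c) = Φ((ln c − ln m)/s), and the expected number of negatives in Arm A is 25 times that. For example, with m = 200 ng/mL and s = 1.2, (ln 0.5 − ln 200)/1.2 = −4.99, so P(below 0.5) is about 0.0000003.

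| Assumed median (ng/mL) | log-SD | Expected below 0.5 ng/mL, of 25 | Above 500 ng/mL | Expected below 500 ng/mL, of 25 |
|---|---|---|---|---|
| 200 | 0.8 | <0.00001 | 12.6% | 21.8 |
| 200 | 1.2 | <0.00001 | 22.3% | 19.4 |
| 500 | 0.8 or 1.2 | <0.00001 | 50.0% | 12.5 |
| 1000 | 0.8 | <0.00001 | 80.7% | 4.8 |
| 1000 | 1.2 | <0.00001 | 71.8% | 7.0 |
| 2000 | 0.8 | <0.00001 | 95.8% | 1.0 |
| 2000 | 1.2 | <0.00001 | 87.6% | 3.1 |

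The first result is not sensitive to the assumed range. To expect even one negative in 25 at 0.5 ng/mL (probability 0.04, z = −1.751), the median would have to be 0.5 × exp(1.751 × s). That is about 2.0 ng/mL for s = 0.8 and 4.1 ng/mL for s = 1.2, roughly 50 to 100 times below the bottom of the assumed range.

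**The 2 by 2 table if all 25 are positive, with 3 VTE.**
- Sensitivity = 3/3 = 100%
- Specificity = 0/22 = 0%
- Positive predictive value = 3/25 = 12%, which is simply the event rate
- Negative predictive value = 0/0, undefined

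**Fine and Gray model at this cut-off.** If the covariate equals 1 for everyone, exp(β) cancels from every term of the partial likelihood, so β cannot be estimated.

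**The other D-dimer cut-offs.** A top-tercile cut leaves two thirds of the cohort negative by construction: 25 × 2/3 ≈ 17 of 25. The 75th-percentile cut leaves 75% of its reference sample negative. Neither depends on the printed unit. The age-adjusted cut-off has no number, formula or unit in the text, so its effect cannot be worked out.

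**The case against.** The strongest reply is that the documents never state the assay's unit, range or expected values. That per millilitre was intended, and that patients lie far above 0.5 ng/mL, are therefore not facts read from the plan. This stands: the first is a probable reading and the second an assumption. A character lost from the electronic text cannot be wholly excluded either, although the micro sign is intact elsewhere in 9.1.

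The internal support is also indirect. Poor specificity, which 9.1 concedes, does not contradict a very low threshold. A reader might take 9.1 to say that the standard cut-off has useful specificity; it says only that specificity is poor. The statement on negative predictive value in 13.6.3 covers microparticles and D-dimer together, in earlier cohorts, and is not tied to the 500 figure. What remains is that ruling out VTE and a high negative predictive value both presuppose a negative class, which the printed value would almost certainly not provide.

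The harm is limited as well. The 2 by 2 table would show an empty row and 0% specificity, so the fault would probably be noticed and not reported as a success. The laboratory could check a threshold labelled as standard before classifying anyone. These points lower the severity, but they do not make the printed constant right.

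**Conclusion.** The point holds as a probable unit error of a factor of 1000 in one pre-defined D-dimer cut-off. Its severity is minor. If D-dimer medians are in the assumed range of 200 to 2000 ng/mL, the printed threshold classifies essentially all patients as elevated and makes the planned assessment at that cut-off uninformative.

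A reader might infer that D-dimer as a marker has no negative class in this trial, that the combined microparticle and D-dimer rule reduces to microparticles alone, or that no Fine and Gray model for D-dimer can be fitted. The documents do not support these readings. The percentile and tercile cut-offs keep negative patients, 13.6.3 does not tie the combined rule to the 500 figure, and the modelling failure is confined to this one classification. The analysis is exploratory (1.3, 13.6), and no primary endpoint, sample size, eligibility criterion or safety rule uses D-dimer.

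**What to change.** Before the stored samples are analysed:

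1. Check the standard cut-off against the assay's reporting unit, including whether results are in fibrinogen-equivalent units.
2. Correct the unit in 9.1. Per millilitre in place of per litre is likely, but the assay documentation should decide.
3. Give the age-adjusted cut-off as a formula in the same unit.
4. Repeat the corrected standard and age-adjusted cut-offs in 13.6.3, so that the pre-defined values stand where they are used. It would also help to give the 75th-percentile value with its unit, and to say which D-dimer cut-off the combined rule uses.

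The cost is a short text correction. D-dimer is measured centrally after the trial ends and is kept out of the medical record, so nothing in trial conduct changes.

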## **9.2 Laboratory Correlative Studies**

### **9.2.1 Microparticles and D-dimer**

#### **9.2.1.1 Collection of Specimen:**

Blood will be obtained by a non-traumatic venopuncture from peripheral veins or from a central venous catheter draws up to 48 hours prior to the first dose of treatment. A total of 10 ml will be drawn into blue top tubes (3.2% citrate) in either two 5ml tubes or one 15ml tube.

9.2.1.2 Handling of Specimens: First centrifugation should be performed within 1 hour of specimen collection. Plasma separated at 2100 x G for 20 minutes. The plasma layer will be centrifuged a second time at 2100 x G x 20 minutes in a single tube. The plasma supernatant will be transferred to a clean tube leaving the 1ml at the bottom of the tube undisturbed (to be discarded). The transferred plasma sample will be aliquoted (500 $\mu$ l) into 1.5ml eppendorf tubes.

Shipping of Specimens: Tubes can be stored locally at -80°C and batch sent on dry ice to:

9.2.1.3 Site Performing Correlative Studies: BIDMC

## 10. STUDY CALENDAR

Baseline evaluations are to be conducted within 48 hours prior to start of protocol therapy.

Event/Procedure	Screening/ Pre-treatment	Day 1	Days 2-6 a	Day 7 a,c	Days 8-13 a	Day 14	Day 17
Day Range	-2 to 0			± 1 day		-4, +7 days	± 5 days
Eligibility Assessments	X						
Informed Consent	X						
Inclusion/Exclusion Criteria	X						
Medical History	X						
ECOG Performance Status Score	X						
Concomitant medication review	X			X		X	
Randomization	X						
Administer enoxaparin		X	X	X	X	X	
Clinical Assessments							
Physical examination including vital signs, and height	X						
Clinical Prediction Score data collection	X						
Weight	X			X			
Assessment of signs and symptoms of VTE and bleeding	X			X		X	
Laboratory Tests							
Plasma storage for correlative studies	X						
Complete blood count	X d	X		X			
PT/PTT	X						
Creatinine	X	X		X			
AST/ALT	X						
Imaging							
Bilateral lower extremity ultrasound							X b

a: Study subjects will only remain on treatment while hospitalized or until day 14, whichever comes first.

b: Arm A ONLY (standard dose enoxaparin).

c: Day 7 study visit not mandatory if participant is no longer hospitalized.

d: Also record CBC from initial admission

## 11. MEASUREMENT OF EFFECT

### Venous Thromboembolism (VTE)

Cumulative incidence of venous thromboembolic events is the primary endpoint for Arm A and a secondary endpoint for Arm B. ***The composite endpoint includes objectively confirmed proximal or distal lower extremity DVT, subsegmental or larger pulmonary embolism; or fatal PE diagnosed by autopsy.*** All other venous or arterial events will be recorded and analyzed as secondary endpoints (including central line associated DVT).

Participants presenting with symptoms compatible with DVT and/or PE will undergo radiographic imaging with compression ultrasound, VQ lung scan, or spiral CT. Confirmed episodes of VTE will be managed by the treating physician per standard of practice.

Presence of any of the following will be considered diagnostic for a VTE:

- New non-compressibility of lower extremity deep venous segments by compression ultrasound.
- Intraluminal defects in two or more views on pulmonary angiography
- Sudden contrast cut-off of one or more vessels greater than 2.5 mm in diameter on a pulmonary angiogram
- A high probability VQ lung scan showing one or more segmental perfusion defects with corresponding normal ventilation (mismatch defect)
- Abnormal spiral CT showing thrombus in pulmonary vessels (subsegmental or larger)

Those VTE that do not qualify for the primary endpoint such as a central line-associated thrombus will be recorded and analyzed as secondary endpoints.

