### 1.2 Primary Objectives

- The primary objectives of the study are to estimate the cumulative incidence of VTE and major hemorrhage in hospitalized cancer patients receiving standard dose or weight-adjusted enoxaparin.

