### **2.3 Rationale**

Based on the available evidence, it is apparent that an accurate assessment of risk versus benefit for primary thromboprophylaxis of hospitalized cancer patients is not possible. It is also evident that hospitalized cancer patients commonly receive pharmacologic thromboprophylaxis without attention to the presence or absence of thrombotic risk factors. In highest risk cancer patients, current pharmacologic regimens are inadequate with as many as 20% patients suffering from thromboembolic events. The principle goals of this phase II clinical trial are to establish a more accurate point estimate of rate of VTE in high risk cancer patients receiving standard, fixed-dose low molecular weight heparin thromboprophylaxis and to develop a point estimate of hemorrhage using intermediate-dose enoxaparin prophylaxis in higher risk patients.

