**5.3 Off treatment procedures (unblinding)**

Following the completion of the day 14 assessment, study staff will contact a clinical research pharmacist at BIDMC. Criteria for off treatment will be reviewed and then the study staff will be informed as to whether the participant was previously assigned to Arm A (standard enoxaparin) versus Arm B (weight-based enoxaparin). For participants randomized to Arm A, a bilateral ultrasound will be scheduled (see study calendar) to evaluate for asymptomatic deep vein thrombosis.

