### **13. STATISTICAL CONSIDERATIONS**

#### **13.1 Study Design/Endpoints**

The primary aim of randomized phase II trial is to estimate the cumulative incidence of VTE and major hemorrhage in hospitalized cancer patients receiving standard dose or weight adjusted enoxaparin.

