### 13.5 Analysis of Primary Endpoints

Cumulative incidence of VTE at day 17 (in arm A) and major hemorrhage endpoints at day 14 (both arms) will be calculated along with their 90% exact binomial confidence intervals.

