### 13.7.2 Evaluation of the Primary Efficacy Endpoint

All participants will be assessed for primary endpoints as long as received at least 1 dose of enoxaparin following randomization.

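### VTE in Arm B is a stated aim and a secondary endpoint on the same composite as Arm A, but only Arm A has the screening ultrasound, so Arm B's composite rate would be biased low; the 13.6.1 power for symptomatic VTE borrows a scan-inclusive rate

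*Combined protocol and SAP*

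**What the plan says.** Section 1.2 sets the primary objectives as to "estimate the cumulative incidence of VTE and major hemorrhage in hospitalized cancer patients receiving standard dose or weight-adjusted enoxaparin". Section 13.1 repeats this: "The primary aim of randomized phase II trial is to estimate the cumulative incidence of VTE and major hemorrhage", again for both regimens. Neither limits VTE to one arm.

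Section 11 (Venous Thromboembolism) separates the arms: "Cumulative incidence of venous thromboembolic events is the primary endpoint for Arm A and a secondary endpoint for Arm B". It then gives a single composite for both: leg DVT, proximal or distal, confirmed by imaging; PE down to subsegmental level; and fatal PE at autopsy. Symptoms are not required. Section 11 also provides imaging for any participant with compatible symptoms, in either arm.

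Section 5.3 provides that, for Arm A, "a bilateral ultrasound will be scheduled (see study calendar) to evaluate for asymptomatic deep vein thrombosis". Footnote b to the section 10 calendar marks that scan "Arm A ONLY (standard dose enoxaparin"). The last scheduled VTE assessment in Arm B is the day-14 symptom check, which section 5.2.3 allows by phone.

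Section 13.5 restricts the primary VTE analysis: "Cumulative incidence of VTE at day 17 (in arm A"), with hemorrhage at day 14 in both arms. This agrees with section 2.3, where one goal is "to establish a more accurate point estimate of rate of VTE in high risk cancer patients receiving standard, fixed-dose low molecular weight heparin thromboprophylaxis" and the other is a hemorrhage estimate on the intermediate dose.

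Section 13.6.1 compares symptomatic VTE, collected before unblinding, between arms. It quotes power of 0.74 for 25% against 0%, one-sided 0.05, and adds a day-17 competing-risk estimate of VTE without naming an arm.

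**The concern.** One endpoint definition is applied to two arms that are examined differently. In Arm A it counts clinically detected events plus those found by the scan. In Arm B it counts only clinically detected events. Section 13.2 itself expects the mandated ultrasounds to raise the observed rate, so the direction of the difference is not in doubt.

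Section 13.4 says the purpose is point estimates of VTE and hemorrhage for planning a larger trial, and that efficacy data will go to the DSMB if the hemorrhage trigger is met. Two places in the text could produce an Arm B rate that is not comparable with Arm A's: the secondary endpoint in section 11, and the day-17 estimate in 13.6.1 that names no arm. Set beside the Arm A figure, such a rate would favor Arm B even with no true effect. If VTE in Arm B really were a primary objective, as 1.2 and 13.1 read literally, the asymptomatic events needed to meet it would not be collected and could not be recovered later.

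The power statement mixes the same two quantities: it is made for symptomatic VTE, but its event rate is taken from an interval for VTE including the scan.

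**Working it through.** **Inputs.** n = 25 per arm (50 in total, 25 on standard dose; 13.2). Day-17 VTE in Arm A 12%, 90% interval 3.3 to 28.2% (13.2). Power 0.74 for 25% against 0%, one-sided 0.05 (13.6.1). The scan-only share f of composite events is not in the documents and is an assumption, taken as equal in both arms.

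**Step 1: the plan's interval.** 12% of 25 is 3 events. The exact (Clopper-Pearson) 90% limits for 3/25 are the 0.05 quantile of Beta(3, 23) and the 0.95 quantile of Beta(4, 22): 3.35% and 28.17%. The stated interval reproduces, apart from truncation of the lower limit. It belongs to day-17 VTE with the scan included.

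**Step 2: what Arm B would record.** With a true composite rate of 12% in both arms, the expected Arm B rate without a screening scan is 12% × (1 − f). Expected events are 25 times that rate, and P(no events) = (1 − rate)^25.

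| f | Arm B rate | Expected events | P(no events) | Spurious A − B gap |
|---|---|---|---|---|
| 0 | 12.0% | 3.0 | 0.04 | 0 |
| 0.25 | 9.0% | 2.25 | 0.09 | 3.0 points |
| 0.50 | 6.0% | 1.5 | 0.21 | 6.0 points |
| 0.75 | 3.0% | 0.75 | 0.47 | 9.0 points |
| 0.90 | 1.2% | 0.3 | 0.74 | 10.8 points |

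The direction holds for any f above 0. Only the size depends on the assumption.

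**Step 3: the plan's power.** The continuity-corrected normal approximation, with d = p1 − p2 and p̄ = (p1 + p2)/2, is

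power = Φ{ [d − 1/n − 1.645 √(2p̄(1 − p̄)/n)] / √([p1(1 − p1) + p2(1 − p2)]/n) }.

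For p1 = 0.25, p2 = 0, n = 25: the numerator is 0.25 − 0.04 − 1.645 × 0.0935 = 0.056, the denominator is 0.0866, the ratio is 0.648 and the power is 0.742. The stated 0.74 reproduces.

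**Step 4: power at a symptomatic rate.** Let s = 1 − f be the symptomatic share of the 25%, and put p1 = 0.25 × s into the same formula. The exact Fisher power is shown alongside. With 25 per arm and no events in Arm B, the one-sided Fisher test needs at least 5 events in Arm A.

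| s | p1 | Continuity-corrected | Exact Fisher |
|---|---|---|---|
| 1 | 25% | 0.74 | 0.79 |
| 0.75 | 18.75% | 0.56 | 0.52 |
| 0.50 | 12.5% | 0.34 | 0.20 |
| 0.25 | 6.25% | 0.11 | 0.02 |

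Both columns assume 0% in Arm B, as the plan does.

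**The case against.** The best defense is that VTE as a primary estimate in Arm A only was intended, and that most of the text says so. Section 2.3 seeks the VTE rate on the fixed dose. Section 11 calls VTE secondary in Arm B. Section 13.5 covers primary endpoints, so leaving out a secondary one is consistent. Section 13.6.1 takes up VTE in Arm B as a secondary analysis. On this view 1.2 and 13.1 are the outliers, and their wording can be read distributively. This largely stands, and the fix adopts it. It does not remove the Arm B composite endpoint in section 11 or the day-17 estimate with no arm named.

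It is also right that the only planned between-arm comparison, in 1.3 and 13.6.1, is already restricted to symptomatic VTE before unblinding. The Arm A scan does not distort it.

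Several stronger readings are tempting but unsupported:

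- That Arm B is never imaged. Symptomatic participants in both arms are; what Arm B lacks is a mandated screening scan.
- That section 13.7.2 promises VTE ascertainment in Arm B. "All participants will be assessed for primary endpoints as long as received at least 1 dose of enoxaparin following randomization" is a rule on who is evaluable and adds little.
- That the phase III trial will be undersized by a known amount. This assumes it is sized from a simple difference in composite rates, which no section plans.
- That the discharge-database rates in section 2.1 (8.1% for pancreatic cancer, 4.1% overall) fix the scan-only share. Dividing them by 12% would mix population and time window with detection.
- That 0.74 is miscalculated. It reproduces; the exact Fisher value of 0.79 reflects a different method.

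**Conclusion.** The concern holds in a limited form. As written, the Arm B composite rate, and any day-17 rate reported for Arm B, is biased low relative to Arm A whenever some events are found only by the scan. Over an assumed scan-only share of 25% to 90%, a true 12% in both arms would appear as 9.0% down to 1.2% in Arm B. The documents support the direction but not a particular value in that range.

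The 13.6.1 power does not belong to the endpoint it is attached to. It is 0.74 only if every event behind the 25% is symptomatic, and 0.56 to 0.11 if 75% to 25% are. The consequence is modest, since the plan says this analysis is not formally powered.

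The Arm A day-17 estimate, the hemorrhage estimates in both arms and the planned symptomatic comparison are not affected. The correction should be made because the study exists to supply planning estimates.

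**What to change.** Changes of wording only:

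- **1.2 and 13.1:** align with 2.3 and 13.5. Day-17 VTE including the scan is primary in Arm A only; day-14 major hemorrhage is primary in both arms.
- **Section 11:** define the Arm B secondary endpoint as symptomatic VTE collected before unblinding, report the same measure for Arm A, and list scan-detected DVT separately as Arm A only.
- **13.6.1, estimation:** limit the day-17 competing-risk estimate to Arm A, and estimate symptomatic VTE before unblinding in both arms.
- **13.6.1, power:** restate it at a symptomatic VTE rate, naming the formula, or delete it.
- **13.4 and phase III planning:** state that any between-arm VTE data given to the DSMB or used to plan phase III rest on the same mode of detection in both arms.

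This adds no patients, scans or data. The price is a less favorable stated power and an explicit acknowledgment that Arm B has no scan-inclusive VTE rate. If the sponsor does intend VTE in Arm B as a primary objective, the ascertainment passages (5.1, 5.3, section 10) must be reconciled with it before enrollment, because the missing information cannot be recovered afterwards.
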